9.2.1. Impact on Study Treatment

The impact the event had on the study treatment will be assessed as either: none, study treatment interrupted, study treatment discontinued, or not applicable. The "not applicable" assessment will be used only when the subject is no longer in the treatment period of the protocol or died.

9.2.2. CTCAE Grade (Intensity) Assessment

The guidelines outlined in CTCAE v5.0 will be used for assessing the intensity of the event. The general guidelines for assessing the AE grade appear below. Full guidelines may be obtained at

https://ctep.cancer.gov/protocolDevelopment/electronic_applications/docs/CTCAE_v5_Quick_Reference_5x7.pdf

Table 9-1: CTCAE v5.0 General Guidelines

Grade	Description
Grade 1	Mild; asymptomatic or mild symptoms; clinical or diagnostic observations only; intervention not indicated.
Grade 2	Moderate; minimal, local or noninvasive intervention indicated; limiting age-appropriate instrumental activities of daily living (ADL)*.
Grade 3	Severe or medically significant but not immediately life-threatening; hospitalization or prolongation of hospitalization indicated; disabling; limiting self care ADL†.
Grade 4	Life-threatening consequences; urgent intervention indicated.
Grade 5	Death related to AE.‡

*Instrumental ADL refer to preparing meals, shopping for groceries or clothes, using the telephone, managing money, etc.

†Self care ADL refer to bathing, dressing and undressing, feeding self, using the toilet, taking medications, and not bedridden.

‡Unlike the AE outcome assessment (see [Section 9.2.5](#)), a subject may have more than one Grade 5 event.

-Common Terminology Criteria for Adverse Events (CTCAE), v5.0: Nov 27, 2017

9.2.3. Causality Assessment

Adverse events will be assigned a relationship (causality) to the study treatment and SOC chemotherapy or radiotherapy. The Investigator will be responsible for determining the relationship between an AE and the study treatment. The type of event, organ system affected, and timing of onset of the event will be factors in assessing the likelihood that an AE is related to the study treatment. Relationship of AEs to study treatment will be classified as follows:

- 1. Unrelated** – The event is definitely not associated with the study biologic or control. Other conditions including concurrent illness, progression or expression of the disease state, or reaction to a concurrent medication explain the reported AE.
- 2. Unlikely** – The temporal association, patient history and/or circumstances are such that the study biologic or control is not likely to have had an association with the observed event. Other conditions including concurrent illness, progression or expression of the disease state, or reaction to a concurrent medication, appear to explain the reported AE.
- 3. Possibly** – The event follows a reasonable temporal sequence from study biologic or control but could have been produced by the patient's clinical state or other therapies administered to the patient.
- 4. Probably** – The event follows a reasonable temporal sequence from the study biologic or control, abates upon discontinuation of the study drug or control, or cannot be reasonably explained by known characteristics of the patient's clinical state.

5. Definitely – The event follows a reasonable temporal sequence from the study biologic or control, abates upon discontinuation and cannot be explained by known characteristics of the patient’s clinical state.

9.2.4. Treatment Given as a Result of the Event

The event impact in terms of treatment provided will be as either: none, medication administered, non-drug therapy administered, surgery performed, hospitalization, or other (with a specification).

9.2.5. Outcome Assessment

The outcome of the event will be assessed as either: resolved, resolved with sequelae, ongoing, or death. Only one AE per subject is allowed to have an outcome assessment as “death.” If there are multiple causes of death for a given subject, only the primary cause of death will have an outcome of death.

9.2.6. Injection-site reactions

Injection-site reactions thought to be directly related to the injection are considered to be AEs of special interest, and will be assessed as per CTCAE v5.0.

For subjects who develop Grade 1 or Grade 2 events, therapy will be continued as per protocol. If a subject chooses to discontinue study treatment, the site should notify the protocol team leadership, and encourage the subject to complete any remaining study visits until the toxicity resolves.

For subjects who develop Grade 3 events following study drug injection, the subject should be reevaluated closely until the AE returns to Grade 1 or less, at which time study treatment may be reintroduced at the discretion of the site investigator. If the same Grade 3 AE recurs following the next administration of study drug, study treatment must be permanently discontinued. Subjects experiencing Grade 3 AEs requiring permanent discontinuation of study treatment should be followed closely for resolution of the AE to Grade 1 or less and the team leadership must be notified.

For Grade 4 events permanently discontinue therapy.

9.3 SERIOUS ADVERSE EVENTS

A SAE is defined as any AE that:

- Results in death
- Is life threatening (the subject is at immediate risk of dying from the adverse experience)
- Requires subject hospitalization or prolongs existing hospitalization
- Results in persistent or significant disability/incapacity

- Is a congenital anomaly/birth defect
- Important medical events that may not result in death, be life-threatening, or require hospitalization may be considered a serious adverse device effect when, based upon appropriate medical judgment, they may jeopardize the subject and may require medical or surgical intervention to prevent one of the outcomes listed in this definition

9.4 REPORTING OF SERIOUS ADVERSE EVENTS

The Investigator is required to report all SAEs that occur during the time period specified in [Section 9.2](#). Once the Investigator becomes aware of an SAE, he/she must report the SAE to [REDACTED] within 24 hours:

CRO Medical Monitor	[REDACTED]
	[REDACTED]

A written SAE reports must include a full description of the event as described in [Section 9.2](#) and must follow within 24 hours from the time the Investigator first learned of the event. The [REDACTED] may request additional supporting documentation as it becomes available, such as lab reports, electrocardiogram [ECG] reports, discharge summary, hospital notes, etc, if applicable.

The Investigator is also responsible for reporting all SAEs to the appropriate Institutional Review Board (IRB) in accordance with local laws and regulations. The Investigator is responsible for maintaining documentation in the study file that indicates the IRB has been properly notified.

9.5 SAE FOLLOW-UP

All subjects experiencing an SAE, including the discontinued subjects, must be closely followed until sufficient information is obtained to indicate a return to normal status or until the event stabilizes at a level acceptable to the investigator (i.e., recovery, return to baseline status, no further improvement expected, or death).

For each SAE indicated as an unresolved event on the initial report, regardless of whether the subject completed the study or withdrew, the site should submit a follow-up report with updated information.

10 DIRECT ACCESS TO SOURCE DATA/DOCUMENTATION

Subjects will be identified on eCRFs by a unique subject identification number and on source documents by name and date of birth. No personal identifier will be used in any publication or communication used to support this research study. The subject identification number will be used if it becomes necessary to identify data specific to a single subject.

The local IRB, FDA, the monitors, auditors and personnel authorized by the Sponsor are eligible to review the medical and research records related to this study as part of their responsibility to protect human subjects in clinical research. They will be given direct access to source data and documentation (e.g., medical charts/records, printouts etc.) for source data verification, provided that subject confidentiality is maintained in accordance with local requirements. Access to electronic medical records may be governed by institution policy and each site will be required to ensure access while remaining compliant with institutional requirements.

11 QUALITY CONTROL AND QUALITY ASSURANCE

11.1 MONITORING REQUIREMENTS

The specific obligations outlined in 21 Code of Federal Regulations (CFR) and ICH guidelines require the Sponsor to maintain current personal knowledge of the progress of a study. Therefore, the Sponsor's designated monitor will visit the site during the study as well as maintain frequent telephone and written communication. The Investigator will permit the Sponsor to monitor the study as frequently as is deemed necessary and provide access to medical records to ensure that data are being recorded adequately, that data are verifiable and that protocol adherence is satisfactory.

As delineated above, the Investigator will permit representatives of the Sponsor and/or designated CRO to inspect all CRFs and corresponding study subject original medical records (source documents) at regular intervals throughout the study. Subject original medical records and other relevant data must be available to support all data recorded in the eCRF. In addition to the original medical records, these data may include but are not limited to study, laboratory reports, etc.

In accordance with federal regulations, site inspections will serve to verify strict adherence to the protocol and the accuracy of the data that is being entered on the case report forms. A Monitoring Log will be maintained at each study site. The Monitoring Log will be signed by the monitor, dated and stated the type of visit. The Investigator should be aware that the study site and subject records may be inspected by the Sponsor and or representatives of the designated CRO, FDA or other regional regulatory authority.

11.2 ACCEPTABILITY OF CASE REPORT FORMS (CRFs)

For each subject who has signed an informed consent form, a CRF must be completed. For subjects who are screen failures, this would be limited to the screen failure CRF page. All source documents and CRFs will be completed as soon as possible after the subject's visit and corrections to data on the CRFs will be documented, if applicable. The Investigator will review the CRFs to indicate that, to his/her knowledge, they are complete and accurate. CRFs will be reviewed by the Sponsor's or designated CRO's monitor, who will make a decision as to their acceptability.

11.3 MODIFICATION OF PROTOCOL

The Investigator will not modify or alter this protocol without first obtaining the concurrence of the Sponsor. Approval by the Investigator's IRB must also be obtained prior to implementation of the change, with two exceptions:

1. When necessary to eliminate apparent immediate hazard to the subject; or
2. When the modification does not involve the subject's participation in the trial.

An amendment may also require modification of the informed consent form. The Investigator will provide an approval letter for the amendment and revised informed consent form, if applicable, to the Sponsor. An amendment must be provided in writing and it must be dated by both the Sponsor and the Investigator. If necessary, the Sponsor will submit protocol amendments to FDA and other appropriate regulatory authorities and notify other Investigators using this protocol.

11.4 REPORTING PROTOCOL DEVIATIONS

The Investigator is obligated to follow the protocol without departure from the requirements written in the protocol. If the Investigator deviates from the protocol requirements, the Sponsor will make the determination as to whether the subject will continue in the study. The Sponsor also has the right to discontinue the subject for protocol violations. The IRB may also have to be contacted if safety to the subject or if the scientific soundness of the study is involved. All protocol deviations must be documented in the CRFs.

11.4.1. Major Protocol Deviation or Violation

A major protocol deviation or violation is a deviation from the IRB approved protocol that may affect the subject's rights, safety, or well being and/or the completeness, accuracy and reliability of the study data. Examples of this include:

- Failure to obtain informed consent prior to initiation of study-related procedures
- A research subject does not meet the protocol's eligibility criteria but was enrolled without prior approval from the sponsor.
- A research subject received the wrong treatment or incorrect dose.
- A research subject met withdrawal criteria during the study but was not withdrawn.
- A research subject received a prohibited concomitant medication.
- Failure to treat research subjects per protocol procedures that specifically relate to primary efficacy outcomes.
- Changing the protocol without prior sponsor and IRB approval.

- Multiple minor violations of the same nature after multiple warnings.

11.4.2. Minor Protocol Deviation or Violation

A minor protocol deviation is any change, divergence, or departure from the study design or procedures of a research protocol that has not been approved by the IRB and which DOES NOT have a major impact on the subject's rights, safety or well-being, or the completeness, accuracy and reliability of the study data. Examples of this include:

- Follow-up visits that occurred outside the protocol required time frame because of the participant's schedule.
- Blood samples obtained at times close to but not precisely at the time points specified in the protocol.

12 DATA SAFETY MONITORING BOARD (DSMB)

The study will be monitored by an independent DSMB to ensure patient safety. The CRO is responsible for the overall management of DSMB, including development of its charter and membership selection. The DSMB will be managed in conformance with the FDA guidelines for DSMB independence, management, and oversight.

The DSMB will consist of at least three members and will review unexpected AEs, related AEs, SAEs, and deaths, according to the study's phase and risk level, as outlined in the DSMB charter.

All expedited safety reports will be provided in real time to the DSMB chair upon being reported to FDA.

Note: For the purpose of expedited safety reporting, all adverse events except skin reactions will be considered unexpected.

The DSMB will make the following recommendations at each safety evaluation:

- Continue the study as planned;
- Assess a specific aspect of safety that is not conclusive;
- Gather more data to address a specific safety issue; and
- Stop the study due to safety concerns.

Additionally, DSMB may recommend protocol modifications or other actions including but not limited to the following:

- Discontinuing or modifying a study based on safety information obtained from the protocol or from information external to the trial
- Changing the eligibility criteria if the risks of the intervention appear to be higher in a particular subset of patients
- Altering the drug dosage and/or schedule if the adverse events observed appear likely to be mitigated by such changes
- Instituting screening procedures that could identify those subjects at increased risk of a particular adverse event
- Identifying information needed to inform current and future trial subjects of newly identified risks via changes in the informed consent document and, if appropriate, recommending re-consent of current subjects to continue trial participation.

The Sponsor retains the responsibility to contact FDA and the final decision regarding the recommendation to continue or to terminate the study.

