1.4.5. PRO 140 1102 Study

For PRO 140 1102, the majority of AEs, other than injection-site reactions, were considered mild and possibly related to drug administration. The majority of injection-site reactions were considered mild, self-resolving, and definitely related to drug administration. PRO 140 derived

from Chinese Hamster Ovary (CHO) cells and administered at 100 mg/mL was generally well tolerated in healthy, normal volunteers. Overall, PRO 140 administered SC using Autoject® 2 appeared better tolerated than manual injection.

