1.4.9. PRO 140 2101 Study

A subcutaneous (SC) form of PRO 140 was tested in HIV-infected subjects. The trial was a randomized, double-blind, placebo-controlled study in subjects (n=44) with early-stage, asymptomatic HIV infection, only R5 HIV-1 detectable, and no antiretroviral therapy for 12 weeks [Thompson, 2009]. Placebo (n=10) and three PRO 140 doses were examined: 162 mg weekly for three weeks (n=11), 324 mg weekly for three weeks (n=11), and 324 mg biweekly (every other week) for two doses (n=12). Subjects were followed for 44 days after the final dose.

Potent, dose-dependent and highly statistically significant antiviral activity was observed. The trial established the first antiviral proof of concept for a long-acting, self-administrable drug for HIV-1 infection [Thompson, 2009].

Subcutaneous PRO 140 was generally well tolerated both locally and systemically. There was no obvious dose-related pattern of toxicity. The most common adverse events (diarrhea, headache, lymphadenopathy and hypertension) were mild to moderate and self-resolving. These events are common in HIV infection and were reported with similar frequencies in the placebo and PRO 140 treatment groups. Administration-site reactions were mild, transient, and observed in a fraction of subjects.

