1.6 RISKS / BENEFITS ASSESSMENT

1.6.1. Risks/Discomfort to Subjects and Precautions to Minimize Risk

Allergic Reaction

Leronlimab (PRO 140) belongs to the monoclonal antibody class of drugs. Monoclonal antibodies are sometimes associated with allergic reactions or flu-like reactions (such as fever, chills, and aches) or injection-site reactions. These events are usually of short duration if they occur at all. Severe allergic reactions, however, can be life-threatening. Although anaphylaxis has not been observed in prior trials of leronlimab (PRO 140), infusion of proteins always carries with it the

theoretical risk for anaphylactic shock. Accordingly, whenever leronlimab (PRO 140) is administered to subjects, there should be available and in place the procedures required to manage anaphylactic shock.

Immune Response

People who take leronlimab (PRO 140) or other monoclonal antibodies can also develop an immune response to leronlimab (PRO 140) that may affect their ability to receive monoclonal antibodies, or to benefit from diagnosis or therapy with a monoclonal antibody in the future.

Pregnancy

Risks to unborn babies are unknown at this time; pregnant females will be excluded from this study. Females of childbearing potential must have a negative pregnancy test prior to enrollment. Both male and female patients and their partners of childbearing potential must agree to use appropriate birth control methods throughout the study duration (excluding women who are not of childbearing potential and men who have been sterilized).

Venipuncture

Blood sampling is required as part of the study protocol. Blood sampling carries a minimal risk of minor discomfort and the possibility of minor bruising at the site of the needle puncture and, rarely, the possibility of infection at the needle puncture site.

Core or excisional biopsy

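### The expedited-reporting note in Protocol Section 12 exempts skin reactions without defining them or limiting them by site, seriousness or severity, so a serious or Grade 4 skin reaction could miss the real-time route to the DSMB chair

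*Protocol*

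**What the plan says.** Three statements in Protocol Section 12 bear on the point.

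- The expectedness note: "For the purpose of expedited safety reporting, all adverse events except skin reactions will be considered unexpected".
- The real-time route: "All expedited safety reports will be provided in real time to the DSMB chair upon being reported to FDA".
- The routine route: the DSMB "will review unexpected AEs, related AEs, SAEs, and deaths, according to the study's phase and risk level, as outlined in the DSMB charter".

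The human data on local reactions are in Section 1.4. For the 1102 study (Section 1.4.5): "The majority of injection-site reactions were considered mild, self-resolving, and definitely related to drug administration". For the 2101 study (Section 1.4.9): "Administration-site reactions were mild, transient, and observed in a fraction of subjects". Section 1.4.14 (CD03) adds that injection-site reactions were similar in frequency and severity at 350, 525 and 700 mg.

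The protocol also provides for worse reactions. Table 6-2 in Section 6.1.5 and Section 9.2.6 both have Grade 3 and Grade 4 entries for injection-site reactions; on Grade 4, Section 9.2.6 says: "For Grade 4 events permanently discontinue therapy". On allergic reactions, Section 1.6.1 says: "Severe allergic reactions, however, can be life-threatening".

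The SAP does not deal with expectedness or expedited reporting.

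**The concern.** An expectedness rule decides which events travel fast. Normally it rests on what has already been seen, in nature and in severity. Here the exception is a whole class of events with no upper limit, while the experience behind it is of mostly mild local reactions. A severe form of a known reaction is new information, and under this note it would be handled like the mild form.

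At stake is how soon the DSMB chair, and FDA through the expedited report, learn of such a case. This matters somewhat more here for two reasons. Section 1.4.3 says that prior exposure was mostly in healthy or HIV-positive subjects, whereas Section 3 allows the drug to be given with standard chemotherapy or radiotherapy. And DSMB review is the main study-level safety check described, with no interval stated: the synopsis says only that it is regular, and Section 12 defers to the charter.

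**Working it through.** No arithmetic applies; the plan gives no figure to reproduce. The check is to set the passages side by side and follow one event through them.

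**What the exception covers, against what supports it**

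| Question | Section 12 note | Experience in Section 1.4 | What the protocol foresees |
|---|---|---|---|
| Site | Any skin reaction | Injection or administration site | Injection site (6.1.5, 9.2.6); allergic reactions listed separately (1.6.1) |
| Severity | No limit | Majority mild (1.4.5); mild and transient (1.4.9) | Up to Grade 4 |
| Seriousness | No limit | No serious injection-site reaction described | A Grade 4 event can meet the SAE definition (9.2.2 with 9.3) |

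No other section of either document defines the exempted term or narrows it.

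**A Grade 4 injection-site reaction followed through the text**

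1. Section 9.2.2 describes Grade 4 as having life-threatening consequences. If the subject is at immediate risk of dying, Section 9.3 makes it an SAE.
2. It is a skin reaction on any ordinary reading, so the Section 12 note leaves it out of the events considered unexpected.
3. The note's stated purpose is expedited reporting. The natural inference is that an event not considered unexpected need not be expedited.
4. Real-time notice to the chair is tied to expedited reports reaching FDA. Without such a report, that notice is not triggered.
5. The other routes do not depend on expectedness. Section 9.4 says: "The Investigator is required to report all SAEs that occur during the time period specified in" Section 9.2. The report is due within 24 hours, the contact shown is the CRO medical monitor, and the IRB must also be told. The DSMB sees the event when it reviews SAEs and related AEs under its charter.

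Step 3 is an inference; the documents do not say outright that an expected event is not expedited. The other steps follow from the text.

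**What is lost.** The loss is the time between the 24-hour SAE report and the next DSMB review, plus the expedited report to FDA. The interval is not in the documents, so no length is given here.

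**The case against.** The strongest reply is that the note is a cautious default. It makes nearly everything unexpected and leaves skin reactions to ordinary assessment; it does not say that a severe one is expected, or that it must not be expedited. Section 13 commits the study to 21 CFR and ICH E6, the charter may add a rule, and nothing bars earlier notice to the chair. Part of this stands: the consequence is inferred and the charter has not been seen. But a site or safety desk following Section 12 alone has no instruction to treat a severe skin reaction differently. If another document is stricter, the note conflicts with it and still needs correcting.

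A second reply is that the SAE, IRB and charter routes remain, and that Section 9.2.6 makes injection-site reactions adverse events of special interest. This stands fully and limits the point to speed.

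A third is that if only serious events are ever expedited, an exception limited to non-serious events does almost nothing. That may be so, but Section 1.4 describes no serious injection-site reaction, so it gives no basis for exempting one.

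Some stronger readings are tempting, and the documents do not support them:

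- *Serious skin events are hidden from the DSMB.* They are not; Section 12 has the board review SAEs and related AEs whatever their expectedness.
- *Worse skin reactions are to be expected because the dose was raised.* Section 1.4.14 reports no increase in their incidence or severity at higher doses, and Section 1.5 reports no dose-proportional increase in adverse events. Nor do the documents show that chemotherapy or radiotherapy makes these reactions worse; that setting is simply less studied.
- *Allergic skin events are exempt.* The wording allows this reading but does not settle it. Section 1.6.1 lists allergic and injection-site reactions separately, and anaphylactic shock is not plainly a skin reaction.
- *Skin is the only class with known drug effects.* Section 1.4.5 also describes other adverse events as possibly related.
- *Subjects would receive a countable number of extra doses before the board acts.* No review interval is given, and Sections 6.1.5 and 9.2.6 hold or stop treatment for the affected subject at Grades 3 and 4.

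**Conclusion.** The point holds as a defect of wording with a limited safety consequence. The Section 12 exception is undefined and wider than the experience it rests on, and the protocol itself foresees reactions beyond that experience. Followed as written, a serious or Grade 4 skin reaction could miss expedited reporting and, with it, real-time notice to the DSMB chair.

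The size is a delay, not a loss of information, and its length cannot be given from the documents. The conclusion rests on two assumptions: that events not considered unexpected are not expedited, which the note implies but does not state; and that the charter, which is not available, does not already require earlier notice. The correction is worth making because it costs little and removes a rule that could send a severe event by the slower route.

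**What to change.** Reword the note in Section 12, for example: *For expedited safety reporting, every adverse event counts as unexpected unless it is a non-serious injection-site reaction of mild or moderate severity that matches, in nature and severity, the experience summarised in Section 1.4. A skin event that is serious, more severe, or away from the injection site counts as unexpected.*

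This settles the scope of the exempted term, including where allergic skin events fall, and brings the note into line with Sections 1.6.1, 6.1.5 and 9.2.6. Make the same change in the DSMB charter. The change concerns reporting only; it leaves dosing and the handling of reactions as they are.

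The cost is a short rewording of one note in the protocol and the matching change in the charter, with possibly a few more expedited reports in a trial of up to 30 subjects.
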